Treatment duration and visits schedule	3 weeks: V1 (D0), V2 (D3±2) and V3 (D21+2 or earlier, as soon as the wound is epithelialized completely) Primary endpoint: Percentage of wound dressing changes associated with a pain <30 mm on VAS at V2 (D3±2). Secondary endpoint • Complete healing at V3 (Day D21+2 or earlier, as soon as the wound is epithelialized completely): Percentage of epithelialization of the wound at V3 calculated based on a blind assessment from photographs using W.H.A.T.						
Treatment duration and visits schedule	3 weeks: V1 (D0), V2 (D3±2) and V3 (D21+2 or earlier, as soon as the wound is epithelialized completely) Primary endpoint: Percentage of wound dressing changes associated with a pain <30 mm on VAS at V2 (D3±2). Secondary endpoint • Complete healing at V3 (Day D21+2 or earlier, as soon as the wound is epithelialized completely): Percentage of epithelialization of the wound at V3 calculated based on a blind assessment from photographs using W.H.A.T. assessment						
Treatment duration and visits schedule	3 weeks: V1 (D0), V2 (D3±2) and V3 (D21+2 or earlier, as soon as the wound is epithelialized completely) Primary endpoint: Percentage of wound dressing changes associated with a pain <30 mm on VAS at V2 (D3±2). Secondary endpoint • Complete healing at V3 (Day D21+2 or earlier, as soon as the wound is epithelialized completely): Percentage of epithelialization of the wound at V3 calculated based on a blind assessment from photographs using W.H.A.T. assessment • Condition of the wound: evaluation by the investigator of 6 condition items at V2 and V3 or Early Termination (ET): bleeding, inflammation, infection, maceration, ratio						
Treatment duration and visits schedule	3 weeks: V1 (D0), V2 (D3±2) and V3 (D21+2 or earlier, as soon as the wound is epithelialized completely) Primary endpoint: Percentage of wound dressing changes associated with a pain <30 mm on VAS at V2 (D3±2). Secondary endpoint • Complete healing at V3 (Day D21+2 or earlier, as soon as the wound is epithelialized completely): Percentage of epithelialization of the wound at V3 calculated based on a blind assessment from photographs using W.H.A.T. assessment • Condition of the wound: evaluation by the investigator of 6 condition items at V2 and V3 or Early Termination (ET):						

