6.2 Secondary study objectives

To compare between the two dressings:

- Complete healing at day 21
- Condition of the wound at study end: overall and according to moisture status at inclusion (e.g. wound shift supporting moist wound healing during treatment)
- Condition of the surrounding skin and efficiency of the CL to drain exudates (exudate management)
- Global satisfaction of user
- Subjects' global assessment
- Safety

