7 INVESTIGATION PLAN AND PROCEDURES

7.1 Overall Design and Flow Chart

This will be a national, multicenter, prospective, randomized in parallel groups, non-inferiority, open-label investigation conducted in France.

Approximately 100 study nurses are planned to participate in the investigation in order to enrol 168 subjects (i.e. 84 per group).

The subjects will be seen for maximum 21 (+2) days and will be followed by their investigator at 3 investigational visits (V): V1 at D0, V2 at D3±2 days and V3 at D21+2 days or earlier, as soon as the wound is epithelialized completely. In case the wound will not fully epithelialized within 23 days or the patient will preliminary discontinue the study treatment for any reason, he or she will receive further treatment of the investigators' choosing according to the actual wound condition and the national standards of care.

Between V2 and V3, additional dressing changes can be performed as often as necessary according to the instruction for use of the investigational product assigned. Lomatuell Pro® and UrgoTul® may be left in place up to 7 days.

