- Assessment of the surrounding skin (inflammatory signs, irritation, allergic rash/eczema, blistering, skin stripping, maceration, dry, trauma to wound edges, product degradation on the skin, hematoma)
- Global assessment of exudate management (efficiency of the CL to drain exudates to the secondary dressing)

The investigator will evaluate the use of the dressing regarding the following parameters:

- Ease of handling
- Ability to maintain its integrity
- Ease of application
- Ability to be repositioned during application
- Conformability
- Wound adhesion

- Ability of dressings to stay in place
- Transparency
- Ease / speed of removal,
- Overall impression,
- Absence of residue

The investigator will apply the allocated investigational product on the wound. If required, 2 investigational products can be used to cover the wound.

A photograph of the wound with the investigational product in place (before the secondary dressing application) will be taken after dressing application according to the photography guidelines.

A secondary dressing could be applied over the investigational product. The type used will be indicated in the CRF by the investigator. The dressing confection will have to follow the condition mentioned in the protocol in section 7.5.

7.2.2.3 Last visit (V3, D21+2 or earlier, as soon as the wound is epithelialized completely)

The last visit must be planned in 21 (+2) days after the first investigational product application (V1, D0), unless the wound is epithelized (one epithelial layer) earlier. In this case the visit should be scheduled shortly after the epithelialization (but not later as in 23 days after the first investigational product application).

Adverse events (AEs) / Serious adverse events (SAEs) / Adverse device effects (ADEs) and Device deficiencies (DDs) occurring since the previous visit will be collected by the investigator. Any changes to the concomitant therapy will also be collected.

Depending on the subject condition, analgesics may be concomitantly prescribed by the investigator. In this case, details on the type of prescribed treatments belonging to analgesic therapeutic class as well as hour of intake before removal (within 2 hours notably) will be recorded in the CRF.

A photograph of the wound with the investigational product in place will be taken before the investigational product removal (but after secondary dressing removal, if there was any), according to the photography guidelines (see Appendix 17.1).

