7.2.2.4 Additional visits

Between V2 and V3, additional dressing changes can be performed as often as necessary according to the instruction for use of the investigational product assigned. Lomatuell Pro® and UrgoTul® may be left in place up to 7 days. In this case, the data collected during these "in-between" visits will be collected in the Nurse Diary.

Data collected during these visits are:

- Number of the additional visit
- Date of the visit
- Reason for dressing change

- Presence of complete re-epithelialization (NB! In case of complete epithelialization all procedures, required for Visit 3 should be performed, data is to be recorded in the CRF section Visit 3 and not as an additional visit)
- Appearance of the dressing before removal
- Bleeding during dressing removal
- Appearance of the wound bed (bleeding, maceration, inflammation, infection, and tissue in-growth in the dressing holes)
- Appearance of the surrounding skin (inflammatory signs, irritation, allergic rash/eczema, blistering, skin stripping, maceration, dry, trauma to wound edges, product degradation on the skin, hematoma)
- Amount of exudate
- Wound moisture
- Local treatment
- Number of dressings used
- Application of dressing
- Secondary dressing
- Initials of person in charge for dressing change

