7.9.1.2 Efficacy analyses

Analysis of the main criterion

The test for the non-inferiority of Lomatuell Pro® vs UrgoTul® for the main criterion will be carried out through a confidence interval (CI) approach. Non-inferiority will be established if the lower unilateral limit of the 97.5% CI in the PP population for the between-treatment difference (Lomatuell Pro® - UrgoTul®) in the percentage of wound dressing associated with a pain < 30 mm on VAS at V2 does not exceed -10%.

Considering that the studied population is "patients with an acute wound" and that the primary endpoint will be assessed at V2 (Day 3±2); we can expect very few drop-outs. We also expect few patients with a major protocol deviation. Therefore, we can conclude that an assumption of 10% attrition rate is acceptable for this study.

In order to unambiguously conclude to non-inferiority in agreement with most of guidelines, the same analysis will be performed on the mITT population. In case of missing data to evaluate the primary criterion, the subjects will be considered as failures. The trial will be considered positive if both approaches support noninferiority.

Adjustment

The frequency of analgesic intake will also be analysed. In case of a significant difference between the 2 dressing groups, the analysis of the primary criterion (painless dressing removals) will be adjusted using a Mantel-Haenszel test.

Analysis of the secondary criteria

The following statistical tests will be used to analyse the secondary criteria according to the criteria type:

- Qualitative nominal criteria will be compared using a Chi² test.
- Qualitative ordinal criteria will be compared using a Mann-Whitney-Wilcoxon test
- Quantitative criteria will be compared using an analysis of variance (ANOVA)

Degree of significance

The criteria for which the degree of significance of the bilateral test will not exceed 0.05 (statistically significant difference) will highlight the specificities between the 2 groups of dressing.

Percentage of complete healing at V3

A wound will be considered as completely healed when there is 100% of epithelialization (first epithelia layer) of the wound. The percentage of wounds healed will be calculated based on a blind assessment from photographs using W.H.A.T.

Assessment of the wound condition

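### Healing is an objective at day 21 but is scored at a V3 that the unblinded nurse can bring forward, so an early photograph read below 100% counts as not healed although day-21 status was never observed

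*Protocol*

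**What the plan says.** - **Objective.** Protocol 6.2 lists "Complete healing at day 21" first among the secondary objectives; the synopsis has the same objective.
- **Who sees the wound.** Protocol 7.1 describes a "non-inferiority, open-label investigation conducted in France". The nurse-investigator therefore knows the dressing.
- **When V3 takes place.** Protocol 7.1 sets "V3 at D21+2 days or earlier, as soon as the wound is epithelialized completely", and "The subjects will be seen for maximum 21 (+2) days". Section 7.2.2.3 plans the last visit for D21(+2) "unless the wound is epithelized (one epithelial layer) earlier". For additional visits, 7.2.2.4 says: "In case of complete epithelialization all procedures, required for Visit 3 should be performed", with the data entered as V3. Section 7.2.2.2 does the same when closure is seen at V2.
- **What is analysed.** Protocol 7.9.1.2 defines complete healing as 100% epithelialization and continues: "The percentage of wounds healed will be calculated based on a blind assessment from photographs using W.H.A.T". Section 7.8.2.2 limits the blinded reading to the V1 and V3 photographs. It also has the investigator judge complete healing at V3 and record it in the CRF, with the blinded reading as an addition.
- **A second form of the variable.** The synopsis gives the endpoint as "Percentage of epithelialization of the wound at V3 calculated based on a blind assessment from photographs using W.H.A.T", which is a continuous percentage per wound, not a proportion of wounds healed.
- **SAP.** Section 4 of the supplied SAP says that it is based on the protocol of another product (Suprasorb C). It contains no rule for this endpoint.

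**The concern.** Two different judgements are joined. The unblinded nurse decides when observation ends; the blinded reader decides whether the wound was healed at that moment. When they agree, nothing is lost. When the nurse calls closure on, say, day 9 and the reader finds less than 100%, the patient has left the trial with up to two weeks of planned observation unused. The scoring definition then places that wound among the failures. A wound that the nurse leaves open is judged at D21 to D23 instead. Two similar wounds can thus be judged at different times because of a decision taken with knowledge of the dressing. Blinding the reading does not undo this, because it does not blind the timing of the photograph.

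At stake is how the healing percentage in each arm can be read against a day-21 objective, and the chi-square comparison at the two-sided 0.05 level that 7.9.1.2 applies to nominal secondary criteria. The wound-closure analysis by baseline exudation in the same section could inherit the problem.

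**Working it through.** **1. Can a discordant early reading be put right within the trial?** No later visit is planned after V3. Table 1 (7.2.1) and Table 2 (7.7) schedule no wound photograph at additional visits. By 7.7, apart from a first shipment after V1 of each site's first patient, pictures leave the site only after its last patient's last visit. The reader's result therefore arrives too late to recall the patient.

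**2. Is there a rule for it?** Section 7.9.1.2 counts missing data as failure for the primary criterion only. No section ranks the investigator's call against the photograph, and none says what day-21 status is when V3 was early. The result of not healed follows from combining the 100% definition with the photograph as the stated basis.

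**3. The plan's own figure.** The only related calculation is the sample size for pain (7.9.2): 95% in both arms (taken as the common rate), margin 10 points, one-sided 2.5%, power 80%.

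n = (1.96 + 0.84)² × 2 × 0.95 × 0.05 / 0.10² ≈ 75 per group; 75 / 0.90 = 83.3, rounded up to 84.

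Both figures reproduce. Neither depends on healing.

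**4. Illustrative size.** The documents give no healing rate, share of early V3 visits or rate of disagreement, so all three inputs are assumptions:

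- e = share of patients whose V3 is early on the nurse's call
- d = share of those whose photograph is read below 100%
- h = share of those discordant wounds that would be closed by D21

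Understatement of day-21 healing = e × d × h.

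| e | d | h | Understatement | Of 84 patients |
|---|---|---|---|---|
| 0.60 | 0.10 | 0.5 | 3 points | 2.5 |
| 0.60 | 0.10 | 1.0 | 6 points | 5.0 |
| 0.40 | 0.05 | 0.5 | 1 point | 0.8 |
| 0.80 | 0.20 | 1.0 | 16 points | 13.4 |

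Setting h = 1 gives the upper bound, since it takes every discordant wound to close in time.

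**5. Between arms.** With e and h equal, the spurious difference is e × h × (difference in d). Assume e = 0.7, h = 0.9, true day-21 healing of 90% in both arms, and 84 per group:

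| d, one arm | d, other arm | Spurious difference | Chance of p < 0.05 |
|---|---|---|---|
| 0.05 | 0.05 | 0 | about 5% |
| 0.05 | 0.10 | 3.2 points | about 8% |
| 0.05 | 0.15 | 6.3 points | about 20% |
| 0.05 | 0.20 | 9.5 points | about 36% |

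With equal discordance the comparison keeps its nominal error rate. The problem between arms exists only to the extent that early discordance depends on the dressing.

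**The case against.** The strongest reply is that the endpoint itself, in the synopsis, in 7.8.2.2 and in the heading within 7.9.1.2, is healing at V3. Read that way, a V3 photograph below 100% is correctly not healed at V3, and only the short wording of the objective says day 21. This stands in part: the documents carry both wordings, so one repair is to reconcile them. It does not remove the point, because the healing percentage is the plan's answer to a day-21 objective, and a V3 whose date depends on an unblinded call does not answer that question for discordant early cases.

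Other parts of the reply also stand:

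- No sentence spells out the discordant case. A reader might take counting it as failure to be an explicit rule; it is a consequence of the definition.
- The investigator's own assessment is already recorded, so the material for a second analysis exists.
- Section 7.8.2.2 regards epithelialization as visible to the naked eye, so the plan expects few disagreements. Section 7.2.2.3 also allows V3 shortly after closure, which in some cases gives the wound a little more time.
- The inputs for the size are assumed, and the upper figures need every discordant wound to close by day 21.

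A reader might infer that the dressing that nurses favour would be penalised. The documents do not support this: they say nothing of nurses' expectations or of how these would affect early calls.

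**Conclusion.** The point holds for a secondary endpoint. The plan's scoring can give a not-healed result against a day-21 objective for wounds never observed at day 21, with the time of assessment set by an unblinded decision, and neither the protocol nor the supplied SAP says how to handle this. On the assumed inputs, day-21 healing is understated by 3 to 6 points in the central illustration and by 1 to 16 points over the wider range. These are illustrations, not estimates. Bias between arms is possible but not shown; it requires early discordance to differ by dressing, and its direction is unknown.

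A reader might go further and doubt the trial's main conclusion. That does not follow: the primary criterion is pain at V2, and both its comparison and the sample size stand apart from the healing endpoint.

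**What to change.** 1. In the synopsis (section 4), 7.8.2.2 and 7.9.1.2, define one binary variable: complete healing by D21(+2), healed if the blinded reading is 100%. Word the objective and the endpoint to match, so that day 21 and an earlier V3 are reconciled. In the same edit, align the V3 window, which 7.8.2.2 once writes as ±2 days where other sections have +2.
2. Keep percentage of epithelialization as a separate descriptive variable.
3. Where V3 was early on the nurse's call and the blinded reading is below 100%, treat D21 status as unobserved. Tabulate these cases by arm.
4. Present the healing comparison twice, with these cases counted as healed and as not healed, and show the investigator's CRF assessment alongside. If the two analyses disagree, describe any dressing difference as sensitive to this handling. Use the same variable in the analysis by baseline exudation.

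The cost is analysis wording and one extra table, and a slightly less definite secondary result. All the data are already planned; no extra visit, photograph or reader is needed. Missing photographs and early terminations are a separate matter that this change does not settle.

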7.2 Procedures and Assessments

7.2.1 Schedule of Assessments

All assessments of the investigation will be conducted as indicated in the following table which displays the frequency and timing of all measurements.

Table 1. Data collection schedule

	Inclusion Intermediate Ad		Additional	Final visit	Early Termination
	visit	visit	visits*	Final visit	visit**
Visit name (corresponding day)	V1 (D0)	V2 (D3±2)	Between V2 and V3	V3 (D21+2 or earlier, as soon as the wound is epithelialized completely)	ET
Oral consent of the patient to	X				
participate					
Inclusion/exclusion criteria	\boxtimes				
Randomization	X				
Demographics	X				
Medical history	X				
Wound/surrounding skin characteristics	×	×	×	X	X
Investigational product application	×	×	×		
Secondary dressing / fixation use	×	×	×		
Dressing removal (to follow the standardized removal procedure)		X	×	X	X
Intake of analgesics	X	×		×	×
Pain assessment (VAS) after application of investigational product	×				
Pain assessment (VAS) during removal		\boxtimes			

Version 2.0 – March 29, 2019

Amount of exudate	X	X	×	X	X
Wound shift (ratio necrotic/ fibrinous/ granulation/ epithelisation tissue)	×	×		X	X
Complete healing assessment		×	×	×	×
Wound photograph	×	×		×	×
Photograph of the investigational product on the wound***	×	×		X	×
Adverse events/Adverse device effects	×	×		×	×
Global dressing investigator evaluation		×		×	×
Global dressing subject's evaluation				X	×
Concomitant treatment	×	X		×	X

^{*} optional, if required by wound's condition

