7.7 Evaluation by W.H.A.T

The evaluation by the W.H.A.T. system will be performed by Lohmann & Rauscher with the photographs sent by RCTs on USB Keys.

For determination of the size of the wound area and recording of occurrence of necrotic/fibrinous/ granulation/ epithelisation tissue the validated Wound Healing Analysing Tool (W.H.A.T.) will be used. The wound dressing should be removed from the lesion. The wound should be cleaned with isotonic saline solution and the rest of remedies should be removed. After cleaning the ruler must be placed close to the wound. To achieve a correct picture, the ruler with the square mark had to be placed in the same plane as the lesion. In the case the wound was not plane the ruler has to be applied in the same shape to allow an authenticable digital reproduction of the wound. One digital picture of the lesion will be taken at each visit (in total three pictures of the lesion for each patient for the whole duration of the study); a minimal resolution of 3.0 million pixels is required.

Also, four digital pictures of the investigational product on the wound should be taken during the study (two photographs will be taken after investigational product application before the secondary dressing application on V1 and V2, and two pictures of the wound with the investigational product in place will be taken before the investigational product removal at both visits V2 and V3 (or Early termination visit, if performed instead of V3).

Table 2. Photographs schedule

Version 2.0 – March 29, 2019

	Inclusion visit (V1)	Intermediate visit (V2)	Additional visits	Final visit, or earlier if epithelization (V3)	Early termination visit (whenever possible)
Picture of the wound with the investigational product in place before the investigational product removal (but after removing the secondary dressing)		х		x	x
Picture of the lesion (after cleaning)	x	х		х	x
Picture after investigational product application before the secondary dressing application	х	х			

The pictures should be saved on a USB Key and sent to Lohmann & Rauscher for assessment. Two shipments of the study pictures are planned:

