The investigator will evaluate the presence of infection at the V1 and at each dressing removal. (According to the investigation plan, presence of the infection is an exclusion criterion and the reason for the discontinuation of the patients from the study).

Necrotic/Fibrinous/Granulation/Epithelisation Tissue ratio

The investigator will assess wound necrotic/ fibrinous/ granulation/ epithelisation tissue ratio at the V1 and at each dressing removal.

In-growth in the dressing holes

The investigator will collect information on the wound tissue in-growth in the dressing holes at the V1 and at each dressing removal.

Surrounding skin condition assessment

Each of the following parameters will be evaluated at V1, V2 (D3±2) and V3 (D21+2 or earlier, as soon as the wound is epithelialized completely) or ET:

Inflammatory signs

(Inflammation is characterized by 4 main signs: erythema, oedema, warmth and pain)

Infection

(Deposition and multiplication of bacteria in tissue with an associated host reaction. The classic local signs of infection include: localised erythema, localised pain, localised heat, cellulitis and oedema; there may also be present specific exudation, smell, delayed healing, abscess, general symptoms. Presence of the infection is an exclusion criterion and the reason for the discontinuation of the patients from the study)

Irritation

(Irritation is synonymous of irritant contact dermatitis which is a secondary inflammation of the skin due to an irritant or caustic agent)

Allergic rash/eczema
 (Cutaneous hypersensitivity reaction induced by a skin contact with an allergenic substance)

Blistering

(Uprising of a part of the epidermis, drawing a projection and thus achieving a bubble that contains a variable fluid)

Skin stripping

(Skin stripping is caused by the repeated application and removal of adhesive tapes and dressings from the skin. This process inflicts variable levels of damage to the layers of the stratum corneum, and may cause inflammatory skin damage, oedematous changes, skin soreness and a detrimental effect on skin barrier function)

Maceration

(Maceration refers to the skin changes seen when moisture is trapped against the skin for a prolonged period. The skin will turn white or grey and will soften and wrinkle)

- Dry
- Trauma to wound edges (Trauma corresponds to underlying lesions or to retraction of wound edges)
- Product degradation on the skin
- Hematoma
- Other

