The wound bed condition will be evaluated at V1, V2 and V3 or ET regarding 6 condition items - bleeding, maceration, inflammation, infection, ratio necrotic/ fibrinous/ granulation/ epithelisation tissue, and tissue in-growth in the dressing holes by means of the following 4-points scale: *none*, *mild*, *moderate*, *severe*. The percentage of each modality for each condition items will be calculated.

Assessment of the surrounding skin condition

The condition of the surrounding skin will be assessed at V1, V2 and V3 or ET regarding different conditions: inflammatory signs, irritation, allergic rash/eczema, blistering, skin stripping, maceration, dry, trauma to wound edges, product degradation on the skin, hematoma, other. These condition items will be assessed by means of the scale *Yes/No*. The percentage of each modality will be calculated.

Wound closure according to inclusion wound exudation status.

This will use a Cochran-Mantel-Haenszel test including treatment groups and baseline wound exudation status (none, light and moderate/heavy).

Global assessment of the dressing by the investigator

The global assessment of the dressing will be performed by the investigator at V2 and V3 or ET. Each item will be evaluated by means of the following scale: *very good, good, poor, and very poor*.

The percentage of each modality of each criterion (ease of handling, ability to maintain its integrity, ease of application, ability to be repositioned during application, conformability, wound adhesion, ability of dressings to stay in place, transparency, ability to transfer wound fluid to the secondary dressing, ease / speed of removal, overall impression, and absence of residue) will be calculated.

Global assessment of the dressing by the subject

A global assessment of the dressing will be performed by the subject at V3 or ET. Each item (ability to maintain its integrity, ability of dressings to stay in place, transparency, comfort of the patient, ability to transfer wound fluid to the secondary dressing, ease/speed of removal, overall impression) will be evaluated by means of the following scale: *very good, good, moderate, poor, very poor.* The percentage of each modality will be presented.

Assessments from the study nurse's booklet at each dressing change

The total number of dressing changes will be calculated and the mean value of dressing changes will be calculated.

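### The four-tissue ratio is to be summarised on a none-to-severe scale that cannot express it, and no analysis of wound shift is defined (secondary endpoint only)

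*Protocol*

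**What the plan says.** The only scale given for the tissue ratio is in Protocol 7.9.1.2, under assessment of the wound condition. Six wound-bed items are named, among them "ratio necrotic/ fibrinous/ granulation/ epithelisation tissue, and tissue in-growth in the dressing holes by means of the following 4-points scale", and the grades are none, mild, moderate and severe. The planned summary is: "The percentage of each modality for each condition items will be calculated". The same section assigns tests to secondary criteria by type: Chi² for nominal, Mann-Whitney-Wilcoxon for ordinal and ANOVA for quantitative data.

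The item has a place in the objectives. The schedule in 7.2.1 labels it "Wound shift (ratio necrotic/ fibrinous/ granulation/ epithelisation tissue" and collects it at V1, V2, V3 and ET. Section 6.2 gives the objective as "Condition of the wound at study end: overall and according to moisture status at inclusion (e.g. wound shift supporting moist wound healing during treatment".

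On measurement, 7.8.2.2 says: "The investigator will assess wound necrotic/ fibrinous/ granulation/ epithelisation tissue ratio at the V1 and at each dressing removal". It names no scale. Section 7.7 provides a second source: for wound area and "recording of occurrence of necrotic/fibrinous/ granulation/ epithelisation tissue the validated Wound Healing Analysing Tool (W.H.A.T.) will be used". On timing it adds: "One digital picture of the lesion will be taken at each visit". The stated uses of W.H.A.T. in analysis are epithelialisation at V3 (synopsis) and the proportion of wounds healed (7.9.1.2).

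**The concern.** Bleeding, maceration, inflammation, infection and tissue in-growth each run from absent to marked, so a 4-point severity scale fits them. The tissue ratio describes how the wound bed is divided among four tissues, two of which (granulation and epithelium) are signs of progress. If the stated rule is followed, a mainly necrotic wound and a mainly granulating wound could receive the same grade, and a between-group comparison of grades would say nothing about which dressing moved the wound bed in the desired direction.

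Wound shift is also a change over time, and the objective asks for it by moisture status at inclusion. If neither is defined in advance, the choice of data source, tissue and contrast is left until after the data are known, in an open-label trial.

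**Working it through.** No figure in the plan depends on this point, so the check is mainly a comparison of sections, with one count to show the mismatch of scale.

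**1. Can the scale hold the information?** Four tissue shares that sum to 100% have three free components. If shares are recorded in steps of 100/k per cent, the number of possible compositions is C(k+3, 3):

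| Step (illustrative assumption) | k | Possible compositions | Grades on the planned item |
|---|---|---|---|
| 50% | 2 | C(5,3) = 10 | 4 |
| 25% | 4 | C(7,3) = 35 | 4 |
| 10% | 10 | C(13,3) = 286 | 4 |

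The loss of detail matters less than the loss of order. Compositions have no single ranking from none to severe. The highest grade would be unfavourable if it referred to necrosis and has no clear meaning for granulation or epithelium.

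**2. Which test would follow?** Read as a 4-grade item, the ratio is ordinal under 7.9.1.2 and goes to Mann-Whitney-Wilcoxon. That test needs an ordering, which this item lacks.

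**3. Does another section give a usable scale?** Protocol 7.2.2.1, 7.2.2.2, 7.2.2.3, 7.2.2.5 and 7.8.2.2 all collect the ratio, and none gives a scale. Section 7.2.2.4 omits it from the data for additional visits, although 7.8.2.2 asks for it at each dressing removal. The CRF is not among the documents.

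**4. Is wound shift defined as a change?** No. The planned summary is the percentage in each grade, with no contrast against V1. The only analysis by baseline wetness is wound closure by exudation status (Cochran-Mantel-Haenszel, 7.9.1.2), which is a different outcome.

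**5. Are the W.H.A.T. tissue data analysed?** In part. Epithelialisation and healing at V3 are covered. No analysis of necrotic, fibrinous or granulation tissue is described at any visit.

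**6. Does the SAP fill the gap?** No. Its section 4 says that it is based on the protocol for Suprasorb C. It plans no formal comparison (section 7.2), and its granulation endpoint is set at W8.

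**7. Is the sample size affected?** No. It rests on the primary endpoint alone: (1.960 + 0.842)² × 2 × 0.95 × 0.05 / 0.10² = 74.6, hence 75 per group, and 75/0.9 = 83.3, hence 84. This reproduces Protocol 7.9.2.

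**The case against.** A reader might infer that the secondary objective on wound condition cannot be answered, or that the photograph-based tissue data are discarded. The documents support neither reading, and the case against them is strong.

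- Wound shift appears in 6.2 only as a bracketed example within a wider wound-condition objective. The other five items under that objective are adequately scaled.
- The synopsis makes epithelialisation at V3 by W.H.A.T. a secondary endpoint, and epithelium is one of the four tissues. The W.H.A.T. data are therefore partly used.
- The general rule in 7.9.1.2 would send tissue percentages, if they are recorded as such, to ANOVA. A test would then already exist.
- Every collection section describes a ratio. The severity scale may be a drafting shortcut, and the unseen CRF may record percentages or grade each tissue separately. In either case the data could be interpreted.

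All four points stand, and they limit the finding to one item. They do not remove it. The one explicit rule for this item is the 4-point scale. The ANOVA rule applies only if that scale is set aside, and it still supplies neither a change from V1 nor a split by moisture.

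The remedy also has uncertainties. Section 7.7 speaks of recording occurrence of the tissues and does not state that a percentage per tissue is produced. It plans a lesion photograph at each visit, but 7.8.2.2 describes the blinded reading for V1 and V3 only.

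**Conclusion.** The point holds for a single secondary item. As specified, the 4-point summary of the tissue ratio is not interpretable at V1, V2 or V3/ET. Wound shift has no defined analysis, either overall or by moisture status at inclusion. Beyond epithelialisation and healing at V3, the W.H.A.T. tissue readings have no stated use. The wider wound-condition objective can still be addressed through the other items, and suitable tissue data may well be collected.

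This conclusion takes 7.9.1.2 as the operative rule. If the CRF records tissue percentages, the fault lies in the analysis text alone. If it records one severity grade, the investigator's data share the fault and only the photographs can repair it. The primary endpoint, its non-inferiority test and the sample size are unaffected. The point is minor but worth correcting before data are seen.

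**What to change.** 1. Remove the tissue ratio from the 4-point list in 7.9.1.2 and keep that scale for the other five items.
2. Analyse the percentage of each tissue as a quantitative variable at V2 and V3/ET, adjusted for the V1 value, and report the between-group difference with its 95% CI. Adjustment for V1 supplies the missing definition of shift.
3. Give the same analysis by baseline moisture, as 6.2 requires. The amount of exudate recorded at V1 is the available measure, and 7.9.1.2 already uses baseline exudation status to stratify wound closure.
4. Name the blinded W.H.A.T. reading as the source, after confirming that it outputs tissue percentages and that V2 photographs are read. Otherwise use the investigator's ratio, recorded as percentages.
5. Because the four percentages sum to 100, the four analyses are not independent. Name one tissue as the main measure and treat the others as descriptive.
6. State how early closure is handled. V3 takes place once the wound has epithelialised, so the epithelial share is 100% by design in wounds that close early. Under 7.2.2.2, a wound already closed at the planned V2 has its data entered as V3, and V2 is marked as not performed.

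The cost is a change of analysis wording, since lesion photographs are already planned at V1, V2 and V3. Extra work arises only if V2 photographs were not going to be read, or if the CRF has to be changed to record percentages.
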